Study Protocol and Statistical Analysis Plan Cover sheet:

Title: Epidermal Permeability Barrier Function and Stratum Corneum Hydration of Rosacea Following Application of Ivermectin

NCT Number: NCT04275999

Date of document: 02/19/2021

Title: Epidermal Permeability Barrier Function and Stratum Corneum Hydration of Rosacea Following Application of Ivermectin

Principle Investigator: [name], PhD

Sponsor or funding source: Galderma

Study Rationale:

Facial erythema is the hallmark of rosacea and the mandatory criterion for its diagnosis.(1) It is estimated that rosacea-related erythema affects more than 40 million people worldwide. The repair and maintenance of the epidermal barrier are critically important in the treatment of rosacea. Rosacea lesions can have a defective barrier, characterized by elevated transepidermal water loss (TEWL) rates and reduced levels of stratum corneum (SC) hydration.(2) The skin barrier function is a critical factor for assessing the severity of rosacea. The precise mechanisms underlying the relationship between rosacea and skin barrier function are not yet known. Some argue that impaired skin barrier function is a consequence of inflammation and continuous stimulation, while others attribute it to infection with follicle mites.(3)

Ivermectin possesses anti-inflammatory by effecting cytokines and neutrophils, and anti-parasitic properties by effecting *Demodex* mites. (4, 5) Ivermectin offers a potential treatment option in maintenance therapy. (6) Recent attention has been directed toward the maintenance and prevention of relapse of rosacea. Treatment with ivermectin may decrease follicle mites, thereby decreasing rosacea flares, improving epidermal barrier dysfunction, reduces TEWL, and improves SC hydration.(7) However, topical application of medications can be complicated, time-consuming, and often frustrating. Poor adherence to therapy can lead to treatment failure and poor health outcomes.(8, 9)

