Frequent office visits improve adherence, but are rarely feasible in everyday practice.(10, 11) Reminders are helpful for patients who are strongly motivated to take the medication but sometimes forget. For the majority of patients, who have not completely bought into the regimen, a subtler approach appears better. This approach aims at building intrinsic motivation, trust, feelings of being cared for, and accountability through frequent contact. In a pilot study of teenagers with acne, sending weekly surveys querying subjects about perceived burden of treatment, perceived usefulness of the medication, current disease severity, and side effects raised mean adherence to 89%, compared to 33% in the control group.(12) The present study aims to validate a very similar tool for patients at risk for low adherence to ivermectin.

Another limitation to improving patients' adherence to topical treatments is that there has not been a practical way to give patients feedback on the state of their skin barrier. Measuring TEWL rates and SC hydration levels could be a valuable tool to give patients this feedback. We propose to test whether we can improve patients' use of topical ivermectin in subjects with rosacea by using a portable hydration measurement device that simultaneously measures both the TEWL rates and SC hydration levels in a study in which we would objectively measuring adherence to daily ivermectin.(13)

Our primary hypothesis is that weekly digital interactions and routine measurement of TEWL rates and SC hydration levels will promote patient adherence to maintenance ivermectin therapy and prevent disease relapse. The project will consist of a trial in which thirty subjects with rosacea receive ivermectin therapy and are randomized to receive either no intervention, a

weekly digital survey to assess patient's attitudes towards ivermectin therapy, or a portal hydration measurement device that measures TEWL rates and SC hydration levels. We will measure adherence objectively in all groups with electronic monitors attached to the containers of the ivermectin, which all subjects will be told to use daily for maintenance therapy. Additionally, the hydration measurement device can transmit data to an Internet server via a smartphone using Bluetooth technology, thereby allowing providers to monitor a patient's TEWL rate and SC levels.

Objectives:

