- Determine the effect of the portable hydration measurement device on treatment adherence to daily ivermectin therapy
- Determine the effect of weekly digital survey on treatment adherence to daily ivermectin therapy
- Determine the effect of daily ivermectin therapy on TEWL rate, SC levels, and rosacea treatment outcomes

Methods and Measures:

Study Design:

Adult subjects will be offered an opportunity to participate in the study. Subjects will either have a diagnosis of rosacea. A total of 30 subjects will be enrolled. After consent and basic demographics, a study team member will use the GPSkin Barrier® to measure the baseline moisture level of the face of all subjects. Subjects will also fill out questionnaires pertaining to quality of life, accountability, patient-physician relationship, and severity of rosacea.

Subjects will be randomized into one of three arms: the control group (n= 10), the digital interaction group (n=10), or the GPSkin group (n=10). All patients will receive ivermectin equipped with an electronic monitor to measure adherence for daily treatment of rosacea. The digital interaction group will receive a survey by email each week asking about their use ivermectin generated by Causa Research. The patients in the GPSkin group will receive the GPSkin Barrier® to measure their moisture level of their face daily. Subjects will be instructed to use the ivermectin once daily. Subjects will return at 3 Months. At this visit, the data from the electronic adherence monitoring will be downloaded, the ivermectin will be weighed, and the patient will fill out the same questionnaires (quality of life, accountability, patient-physician relationship, and severity of rosacea). The intervention subjects will be evaluated on their use of the GPSkin Barrier® to measure their stratum corneum hydration. Participants not randomized to the email intervention group will receive an accountability questionnaire at the beginning and end of the study.

Setting

The study will be conducted at Department of Dermatology at Wake Forest School of Medicine. Data will also be analyzed at Department of Dermatology at Wake Forest School of Medicine.

Subject Selection

Inclusion Criteria

- Subject is 18 years of age or older.
- Subject has a working knowledge of English.
- Subject with a diagnosis of Rosacea
- Subjects without a known allergy to ivermectin
- Subjects with access to a smart phone

Exclusion Criteria

- Subjects under 18 years of age.

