- Subject does not have a working knowledge of English.
- Subject with a diagnosed skin condition other than rosacea
- Subjects with a known allergy to ivermectin
- Subjects without access to a smart phone

Intervention and Interactions

Patients will be recruited from the Dermatology Clinic or from the Dermatology Clinic Database. Team members can recruit in-person with patients in the Dermatology Clinic, or by calling patients with a diagnosis of Rosacea (ICD 10: L71.9). Patients will then be brought to the Center for Dermatology Research for their initial screening visit. Demographic data collected from the patient includes sex, age, and ethnicity.

Outcome Measure

Outcomes include adherence (as measured by electronic monitoring), weight of the ivermectin, rosacea severity, quality of life, reporting of adverse effects, accountability questionnaire, and use of the GPSkin Barrier® in the GPSkin group. Data from the clinical study will be analyzed by a biostatistics software. Correlation between demographics will be measured.

Analytical Plan

Data will be analyzed using descriptive statistics on a biostatistics software.

Human Subjects Protection

Subject Recruitment Methods

Subjects who meet the inclusion and exclusion eligibility criteria will be able to participate in the study. Subjects are recruited at a clinic in the Department of Dermatology at Wake Forest School of Medicine or through the Department of Dermatology Database.

Informed Consent

Informed consent will be acquired for this study. The risk of harm or discomfort is not expected to be more than a daily life or routine physical or psychological exam or test. Rights and welfare of subjects will be protected through the use of measures to maintain the confidentiality of study information. No identifying information will be taken from the patient. The only information taken from the patient includes age, gender, ethnicity, location of the skin lesion, and email addresses. The information collected for this research study includes quality of

life, accountability, and severity of rosacea information. Results of the study will be published or presented in lieu of providing individual subjects additional information regarding the study.

Confidentiality and Privacy

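### The title and the barrier part of the third objective need TEWL and SC hydration after treatment, but no staff reading is planned after baseline, leaving 20 of 30 subjects with no planned follow-up value

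*Combined protocol and SAP*

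**What the plan says.** The title announces the subject: "Epidermal Permeability Barrier Function and Stratum Corneum Hydration of Rosacea Following Application of Ivermectin". The third item under Objectives is: "Determine the effect of daily ivermectin therapy on TEWL rate, SC levels, and rosacea treatment outcomes".

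Study Design sets the sample and allocation: "A total of 30 subjects will be enrolled", randomized to "the control group (n= 10), the digital interaction group (n=10), or the GPSkin group (n=10"). At entry, "a study team member will use the GPSkin Barrier® to measure the baseline moisture level of the face of all subjects". That sentence speaks of moisture only. Study Rationale describes the instrument as a "portable hydration measurement device that simultaneously measures both the TEWL rates and SC hydration levels", so a baseline TEWL value can be inferred but is not stated.

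After baseline, only the GPSkin group keeps a device, for daily self-measurement. There is one return visit, at 3 months, with these procedures: "At this visit, the data from the electronic adherence monitoring will be downloaded, the ivermectin will be weighed, and the patient will fill out" (a repeat of the baseline questionnaires). The visit's one device item is an evaluation of how the intervention subjects used the GPSkin Barrier. No reading is specified.

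Outcome Measure begins: "Outcomes include adherence (as measured by electronic monitoring), weight of the ivermectin, rosacea severity, quality of life, reporting of adverse effects". It goes on to the accountability questionnaire and to device use in the GPSkin group. Neither a TEWL nor a hydration value appears. Informed Consent lists quality of life, accountability and severity as the study information to be collected, and no barrier readings. Analytical Plan is a single sentence specifying descriptive statistics.

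**The concern.** An effect of treatment on TEWL and hydration cannot be described without a value taken after treatment. Study Design lists what is repeated at 3 months, and the GPSkin reading is not on that list. Staff who follow the procedures as written would finish the study with a baseline reading and nothing to compare it with in two of the three arms.

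The third arm does not fill the gap well. Its follow-up values would be taken by the subject at home, while its baseline is taken by a team member, so operator and setting change along with time on treatment. The same arm receives the device as its adherence intervention, so any change there mixes ivermectin use with the influence of device feedback. The plan gives no time window, endpoint or summary rule for the home readings, and it describes their transmission only as something the device can do.

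At stake is whether the study can report what its title promises. A 3-month reading that is not taken cannot be recovered later.

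**Working it through.** **Step 1. The plan's own figure.** The arm sizes in Study Design are 10 (control), 10 (digital interaction) and 10 (GPSkin). 10 + 10 + 10 = 30, which agrees with the stated enrolment. The plan has no power or precision calculation, so there is nothing else to reproduce.

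**Step 2. Planned barrier readings by arm.**

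| Arm | n | Baseline | After baseline | Staff reading at 3 months |
|---|---|---|---|---|
| Control | 10 | staff | none planned | none listed |
| Digital interaction | 10 | staff | none planned | none listed |
| GPSkin | 10 | staff | daily, self-taken at home | none listed; device use evaluated |

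**Step 3. Subjects with no planned follow-up reading.** Control 10 + digital interaction 10 = 20, and 20/30 = 66.7%. At most 10/30 = 33.3% can have any follow-up value, all of them self-taken.

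**Step 4. Which parts of the third objective are affected.** The objective has three components: TEWL, SC levels and rosacea treatment outcomes. The severity questionnaire is completed at baseline and at 3 months in every arm, so the last component has paired data in all 30 subjects as planned. Only the two barrier components lack a planned follow-up.

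**Step 5. Precision, for illustration only.** The plan gives no SD, so the result is in units of the SD of within-subject change. The 95% CI half-width for a mean change is t(0.975, n−1)/√n.

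- n = 10: 2.262/3.162 = 0.715, about 0.72 SD.
- n = 30: 2.045/5.477 = 0.373, about 0.37 SD.
- Ratio: 0.373/0.715 = 0.52, so the interval is about half as wide.

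This assumes no dropout, all three arms pooled as one sample, the same SD of change for home and staff readings, and one follow-up value per subject. With an assumed 10% dropout the half-widths are 0.77 (n = 9) and 0.40 (n = 27). With an assumed 20% they are 0.84 (n = 8) and 0.42 (n = 24).

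**The case against.** The strongest reply is that the plan is silent rather than prohibitive. It does not rule out a second reading, and an outcome list introduced by a word such as include need not be complete. A baseline reading in every subject has little purpose without a repeat, so this may be a drafting omission. That stands to this extent: a reader might infer that the control and digital subjects will never be measured again, and the documents support only that no such reading is planned. But the reading is missing from the visit procedures as well as from the outcome list, so a team working from this text would have no instruction to take it.

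A second reply is that the intervention subjects evaluated at 3 months might include the digital arm. Only the GPSkin group is given a device, however, and Outcome Measure confines the item to that group. What is evaluated is use, not a measured value. Even on the generous reading, the 10 control subjects have no planned follow-up.

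A third is that the primary hypothesis concerns adherence and relapse, and two of the three objectives concern adherence alone. That is correct. The gap touches part of one objective, although it is the part named in the title.

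Two stronger readings are tempting and not supported. One is that the third objective fails as a whole. It does not, because severity is collected at both visits in all arms. The other is that the main harm is the loss of a between-arm comparison of barrier function. No objective asks for that comparison.

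Finally, the precision figures can be challenged. Pooling sits awkwardly with a hypothesis that adherence will differ by arm, and averaging daily home readings could reduce measurement noise. Both criticisms are fair, and the finding does not depend on those figures.

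**Conclusion.** The concern holds for the TEWL and SC hydration part of the third objective and for the title. Of 30 subjects, 20 (67%) have no planned reading after baseline. The other 10 have only home readings that differ from baseline in operator and setting and come from the arm that also receives device feedback. This is more than missing detail, because carrying out the visit procedures exactly as written leaves the barrier question unanswerable in two arms.

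The count rests on reading the 3-month procedures as the full list of what staff do at that visit, and on the GPSkin group being the only one that keeps a device. That baseline TEWL is recorded at all is an inference from what the instrument measures. The half-widths of 0.72 and 0.37 SD are illustrative and carry the assumptions stated with them.

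A reader might also infer that a follow-up reading in all arms would establish the effect of ivermectin on barrier function. It would not. Every arm receives ivermectin and there is no untreated comparison, so even complete data give a before-after change.

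**What to change.** In Study Design, state that a study team member records both TEWL and SC hydration with the GPSkin Barrier in all subjects in all three arms, at baseline and at the 3-month visit. Define one facial site and one set of measurement conditions and apply them at both visits. The current text says only that the face is measured, so an instruction to match baseline would have nothing to match.

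In Outcome Measure, add change from baseline to 3 months in TEWL and in SC hydration. Home readings in the GPSkin arm may be kept as secondary data.

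In Objectives and in the report, describe the result as an uncontrolled before-after change under ivermectin.

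The cost is one short non-invasive reading per subject at a visit already scheduled, with a device that staff already use at baseline, plus a few sentences of protocol text. Assignment, treatment and the visit schedule do not change.

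### The plan specifies only descriptive statistics (plus a correlation between demographics), so no between-arm inference is prespecified for the primary hypothesis or for Objectives 1 and 2, although the design would support it.

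*Combined protocol and SAP*

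**What the plan says.** The combined protocol and SAP sets an inferential aim in three places.

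- Study Rationale, on purpose: "We propose to test whether we can improve patients' use of topical ivermectin in subjects with rosacea".
- Study Rationale, on the hypothesis: "Our primary hypothesis is that weekly digital interactions and routine measurement of TEWL rates and SC hydration levels will promote patient adherence". The same sentence adds prevention of disease relapse.
- Objectives: the first is "Determine the effect of the portable hydration measurement device on treatment adherence to daily ivermectin therapy" and the second is "Determine the effect of weekly digital survey on treatment adherence to daily ivermectin therapy".

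Under Study Design, "A total of 30 subjects will be enrolled", with 10 subjects in each of the control, digital interaction and GPSkin groups. Adherence is recorded by an electronic monitor in all three groups and downloaded at the 3-month visit.

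The analysis text is much shorter. The Analytical Plan reads in full: "Data will be analyzed using descriptive statistics on a biostatistics software". The Outcome Measure section adds "Correlation between demographics will be measured". It opens its outcome list with "Outcomes include adherence (as measured by electronic monitoring), weight of the ivermectin, rosacea severity, quality of life, reporting of adverse effects", then adds an accountability questionnaire and use of the device in the GPSkin group. None of the seven outcomes is ranked or called primary. The document gives no alpha, test, model, confidence interval, analysis set, missing-data rule, multiplicity rule or sample-size calculation.

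**The concern.** Objectives 1 and 2 are comparisons of randomised arms: GPSkin against control, and digital survey against control. Followed literally, the plan produces three sets of arm summaries and stops. It does not say how large either effect is or how uncertain it is. With 10 subjects per arm, means can differ widely by chance, and unaccompanied arm means hide that.

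A between-arm test could still be added later, but it would then be chosen after the data were seen. At most six of the seven listed outcomes can be compared between arms, because use of the device exists only in the GPSkin group. Six outcomes and two contrasts give 6 × 2 = 12 possible comparisons. That is before any choice between monitor records and product weight as the adherence measure, or any choice of how to summarise the monitor records. A result picked from that set would be weak evidence for a stated primary hypothesis.

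**Working it through.** **What the plan's own figures allow.** The only design figure is the sample size: 3 arms × 10 = 30, which agrees with the stated total. With no alpha, power, effect size, SD or dropout rate given, 30 cannot be derived from any formula.

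**Aims set against analyses.**

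| Stated aim | Comparison implied | Analysis planned |
|---|---|---|
| Objective 1, device and adherence | GPSkin vs control | descriptive only |
| Objective 2, survey and adherence | digital vs control | descriptive only |
| Primary hypothesis, adherence limb | the same two contrasts | descriptive only |
| Primary hypothesis, relapse limb | undefined | none; relapse is not a listed outcome |

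The correlation between demographics fills none of these cells.

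**What a prespecified contrast would deliver.** This is an illustration, not a design calculation. Inputs from the documents: n = 10 per arm, and a 56-point gap (89% minus 33%) in a cited pilot of teenagers with acne. That gap is background and not a design assumption. Inputs assumed here: SD of percent adherence 20 to 35 points, equal in both arms; no missing data; two-sample t-test, two-sided, with 18 degrees of freedom.

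95% CI half-width = t(0.975, 18) × SD × √(2/10), where t = 2.101:
- SD 20: 2.101 × 20 × 0.447 = 18.8 points
- SD 35: 2.101 × 35 × 0.447 = 32.9 points

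Pooling the variance over all three arms (27 degrees of freedom) gives 18.4 to 32.1, a negligible change.

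Power comes from the noncentral t distribution with noncentrality (difference / SD) × √(10/2). For half the pilot gap, 56 / 2 = 28 points:

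| SD | difference / SD | power, alpha 0.05 | power, alpha 0.025 |
|---|---|---|---|
| 20 | 1.40 | 84% | 75% |
| 25 | 1.12 | 66% | 54% |
| 30 | 0.93 | 51% | 38% |
| 35 | 0.80 | 40% | 28% |

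The 0.025 column is the level that Holm's procedure applies to the smaller of two p-values.

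For the full 56 points, power at SD 20 to 30 is 98% to over 99% at alpha 0.05, and 95% to over 99% at 0.025. SD 35 is left out here because a 0–100% measure with mean 89% can have an SD of at most √(89 × 11) = 31.3 points.

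The smallest difference with 80% power is 1.325 SD at alpha 0.05 (26 to 46 points over SD 20 to 35) and 1.484 SD at 0.025 (30 to 52 points).

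**Multiplicity.** Two unadjusted 5% tests have a familywise error of at most 0.05 + 0.05 = 0.10. Simulation with the shared control arm gave 0.089.

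**The case against.** The strongest reply is that a trial of 10 per arm, with no power claim, alpha or success criterion, is effectively exploratory, and that description is a sensible analysis at that size. Part of this stands: the intervals will be wide and a confirmatory claim would be fragile. But the document uses the word pilot only for cited studies, never for this trial, and it states a primary hypothesis and an intention to test. Even an exploratory trial with these objectives needs the arm differences and their intervals. Either the aims or the analysis must change.

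A reader might infer two stronger criticisms that the documents do not support.

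- That the trial is incapable of testing its hypothesis. Subjects are randomised and adherence is monitored electronically in all arms, so the data would support a test. What is missing is its specification.
- That the hypothesis concerns a combined intervention that no arm receives, because it joins the survey and the measurements with an 'and'. The sentence that follows assigns subjects to nothing, the survey or the device, and the objectives treat the two effects separately. The wording is loose, but read distributively it fits the design.

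It is also fair to say that Holm adjustment and a permutation test are choices. The essential change is the two adherence differences with confidence intervals.

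**Conclusion.** The point holds as a gap in the written plan: no between-arm inference is prespecified for the primary hypothesis or for Objectives 1 and 2. That conclusion rests on the text alone and needs no assumption.

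The size of the uncertainty does depend on assumptions. For SDs of 20 to 35 points and complete data in 10 subjects per arm, each adherence difference would carry a 95% CI half-width of about 19 to 33 points, and power for 28 points would be 40% to 84% at alpha 0.05 or 28% to 75% at 0.025. An effect as large as the cited acne pilot's would probably be detected; half of it would be missed often under most of these SDs. It would therefore be wrong to infer that the design is futile. It would be equally wrong to present arm means without their imprecision.

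**What to change.** Replace the Analytical Plan sentence with a short paragraph that does the following.

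- **Primary outcome:** electronically monitored adherence, as the percent of days from dispensing to the 3-month visit with at least one recorded opening.
- **Contrasts:** digital vs control and GPSkin vs control, each as a difference in means with a 95% CI and a two-sided test. A permutation test suits small arms and a bounded percentage. If confirmatory claims are to be made, adjust the two tests by Holm's method.
- **Analysis set:** all randomised subjects with monitor data, in the arm assigned. Report by arm the number without data, since the download depends on the 3-month visit. Add a simple sensitivity analysis for them, for example setting their adherence to the lowest and then the highest value observed.
- **Other outcomes:** label all of them secondary or exploratory.
- **Relapse:** either define it from the rosacea severity scores already collected at baseline and 3 months and make it secondary, or remove it explicitly from the primary hypothesis.
- **Hypothesis:** reword it as two separate comparisons, to remove the loose 'and'.

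If the sponsor prefers an exploratory study, say so in the hypothesis and objectives, and still report the two differences with CIs.

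The cost is a paragraph of text and a little analysis, with no new subjects, visits or measurements. If Holm is used, its first step costs roughly 9 to 13 percentage points of power for a 28-point difference (for example 84% to 75% at SD 20, and 40% to 28% at SD 35). The report should describe the results as imprecise.
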